9.3. Continuous Efficacy Endpoints

For continuous efficacy endpoints, the number of patients (n), mean, standard deviation (SD), standard error (SE), median, minimum and maximum will be presented for the actual values and change from baseline at all scheduled visits. It is noted that percent change from baseline may be displayed for certain endpoint variations, based on the TFL shell specifications. 95% CI presented in efficacy graphs will be computed using the t distribution.

All continuous efficacy endpoints will be tabulated by scheduled visit. This includes (see [Table 3](#)) Endoscopic Change, CDAI Change, GHAS Change, RHI Change, CRP Change, and FCP Change. Per Section 5.5.3, efficacy data will be associated with Visits according to analytic visit windows.

In all cases, the primary analysis will be based on observed cases.

The list of continuous efficacy endpoints is shown in [Table 5](#) below:

Table 5. Continuous Endpoints and Imputation Methods

Continuous Efficacy Endpoints	Method(s)
Endoscopic Change (Paired Segments, Total Score)	OC
CDAI Change	OC
SF Change	OC
AP Change	OC
GHAS Change from Baseline (Paired Segments, Total Score)	OC
RHI Change from Baseline (Paired Segments, Total Score)	OC
C-RP Change from Baseline	OC
FCP Change from Baseline	OC
Global RHI Score	OC

10.1.1. Incidence of Treatment Emergent Adverse Events

In the tables showing incidence by SOC and PT, SOCs will be sorted by the alphabetical order and PTs will be sorted within SOC in descending order of incidence. For tables showing incidence by PT only, the PTs will be sorted in descending order of incidence.

An overall summary of TEAEs will show the number and percentage of the patients experiencing TEAEs in following categories

- At least one TEAE
- At least one Moderate or Severe TEAE
- At least one Severe TEAE
- At least one Possible, Probable or Related TEAE
- At least one Related TEAE
- At least one Serious TEAE
- At least one Possible, Probable or Related Serious TEAE
- At least one Related Serious TEAE
- At least one TEAE Leading to Discontinuation of Study Drug
- At least one TEAE Leading to Study Withdrawal
- Death
- Death - Possible, Probable or Related to Study Drug

The incidence of all TEAEs along with number of events will be presented by SOC and PT and, separately by PT only and sorted in descending order of number of patients experiencing the TEAE.

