7.1.2. Extension Period

All patients will receive RPC1063 1 mg daily dose in the Extension Period and may receive treatment through Week 160. During the Extension Period, the investigator should continue to assess the patients clinical status and based on clinical judgment determine if the patient should continue or withdraw from the trial and receive alternative therapy. Extension Period visit schedule and procedures, including early termination and safety follow-up, are provided in [Table 3](#).

Patients who complete the Week 160 visit may have the option to immediately enter (without completing the 30-day or 90-day Safety Follow-up Visits) the open-label extension Phase 3 CD Study [REDACTED].

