3.2. Extension Period Primary Objective

To characterize the long term safety of continued dosing of RPC1063.

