5. GENERAL STATISTICAL CONSIDERATIONS

All efficacy and safety data will be listed by patient. Listings will be sorted by patient number and visit/study day.

Continuous data will be summarized using descriptive statistics: number of patients (n), mean, standard deviation (SD), standard error (SE), median, minimum and maximum.

Categorical data will be summarized using the number and percent of patients. When count or frequency data are presented, the percent will be suppressed when the count is zero in order to draw attention to the non-zero counts. A row denoted “Missing” will be included in count tabulations where necessary to account for dropouts and missing values. The denominator for percentages will be the number of patients within the population of interest, unless otherwise stated. Denominator for percentages in demographic and baseline categories will use the number of non-missing values. Non-zero percentages will be rounded to one decimal place, except 100% will be displayed without any decimal places.

Additional rounding rules are as follows:

- If the original value has 0 decimal places: mean, median, and CIs will have one decimal place and SD will have 2 decimal places;
- If the original value has 1 decimal place: mean, median, and CIs will have 2 decimal places and SD will have 3 decimal places; and
- If the original value has 2 or more decimal places: mean, median, CIs, and SD will all have 3 decimal places.

Minimum and maximum will always have the same decimal places as the original measure, up to a maximum of 3 decimal places.

Unless otherwise indicated, values that are collected with “<” sign and a numerical bound will be analyzed as half the numerical bound, without the sign in tables and figures. Values that are collected with “>” sign and a numerical bound will be analyzed as the numerical bound, without the sign. In listings, these data will be reported as collected, with the sign.

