5.4. Analysis Populations

All patients who are enrolled in the Induction Period and receive at least one dose of investigational drug will comprise both the Intent-to-Treat (ITT) population and the Safety population. Because this is a single arm open label study, these two analysis populations are indistinguishable. This population will be used to summarize all efficacy and safety data for both Induction and Extension Periods.

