8.2.1. Extent of Exposure

Extent of exposure will be summarized for the Safety Population and will include the following:

- Duration of Exposure (Person-Years)
- Number of capsules administered

These outcomes are derived using data as collected in the EDC system. Duration of Exposure in person-years is calculated per-patient as $((\text{Date of Last Dose} - \text{Date of First Dose}) + 1)/365.25$. The number of capsules administered per-patient is directly obtained from the EDC system.

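### In the legible text, adverse events are summarised with no time denominator and no Induction/Extension split, so the planned percentages describe the cohort but do not estimate long-term risk

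*SAP*

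**What the plan says.** - **Objective.** SAP 3.2 gives the Extension's primary objective: "To characterize the long term safety of continued dosing of RPC1063". Protocol 6.1.3 agrees.
- **Statistic.** SAP 10.1.1: "An overall summary of TEAEs will show the number and percentage of the patients experiencing TEAEs in following categories". It adds: "The incidence of all TEAEs along with number of events will be presented by SOC and PT". SAP 10.1.4 (SAEs), 10.1.5 (discontinuations) and 10.1.7 (AESIs) call for summaries by SOC and PT, or by PT, and name no statistic.
- **Denominator.** SAP 5: "The denominator for percentages will be the number of patients within the population of interest, unless otherwise stated". SAP 5.4 defines the safety population as "All patients who are enrolled in the Induction Period and receive at least one dose of investigational drug", and states: "This population will be used to summarize all efficacy and safety data for both Induction and Extension Periods".
- **Length of treatment.** Protocol 7.1.2: "All patients will receive RPC1063 1 mg daily dose in the Extension Period and may receive treatment through Week 160". Withdrawal is at the investigator's clinical judgment throughout, and Protocol 8.3 says that withdrawn patients are not replaced.
- **Exposure.** SAP 8.2.1 derives person-years per patient from first dose to last dose. The abbreviation list defines PYE, but the legible text does not use it.
- **Event collection.** Protocol 12.2.1 collects AEs up to and including the 90-day Safety Follow-up Visit. The treatment-emergent definition in Protocol 13.5 has no end date.
- **Lost text.** The supplied SAP breaks off at Table 6 in Section 9.4 and resumes inside the treatment-emergent definition. The lead-in to Section 10 and the start of 10.1 cannot be read. Sections 10.1.1 to 10.1.7 appear complete.

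**The concern.** A patient who stops after a few days and one treated for three years count equally in the denominator, but the first had little time in which to have an event. The crude percentage therefore mixes how often events occur with how long patients stay. The more patients leave early, the lower it falls at the same underlying event rate.

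This matters most for the Extension. Its primary objective is long-term safety, yet no legible adverse-event summary isolates that period or refers to a defined length of treatment. Length of follow-up affects the reading of any AESI that may arise late, such as malignancy or opportunistic infection. A reader who wants the risk over one year or three, or who sets Extension against Induction, could not obtain it from these tables.

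**Working it through.** **The plan's own figures.** The documents give no precision or rate for safety. Their only precision figures are the efficacy half-widths in SAP 5.1. The formula 1.96 × √(p(1−p)/n) gives 12.8% (p = 0.15) and 16.4% (p = 0.30) for n = 30, and 9.0% and 11.6% for n = 60. All four values match. None bears on safety.

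**Inputs from the documents.** About 60 patients (SAP 5.1). Longest treatment 160 weeks: T = 160 × 7 / 365.25 = 3.07 years. Shortest: one dose, 1/365.25 = 0.003 years. Maximum total exposure: 60 × 3.07 = 184 patient-years.

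**Assumptions (not in the documents).** A constant event rate λ, a constant dropout rate μ, a Week-160 risk of 20%, and retention to Week 160 of 90%, 50% or 10%.

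**Step 1: crude percentage by retention.**

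- λ = −ln(0.80)/3.07 = 0.0728, or 7.28 per 100 patient-years.
- μ = −ln(retention)/3.07.
- Crude percentage = λ/(λ+μ) × (1 − e^(−(λ+μ)T)). Here e^(−(λ+μ)T) = 0.80 × retention.

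| Retention | μ | Calculation | Crude % | Total exposure, 60 patients (patient-years) |
|---|---|---|---|---|
| 90% | 0.034 | 0.679 × (1 − 0.72) | 19.0 | 175 |
| 50% | 0.226 | 0.244 × (1 − 0.40) | 14.6 | 133 |
| 10% | 0.751 | 0.088 × (1 − 0.08) | 8.1 | 72 |

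Patients with an event divided by time at risk to first event gives 7.28 per 100 patient-years in every row.

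**Step 2: allowing for the 90-day follow-up.** Step 1 ends observation at dropout. If every patient is followed for a further 90 days (0.246 years) at the same rate, the event-free share is multiplied by e^(−0.0728 × 0.246) = 0.982.

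- 90% retention: 1 − 0.982 × 0.810 = 20.5%.
- 50% retention: 1 − 0.982 × 0.854 = 16.1%.
- 10% retention: 1 − 0.982 × 0.919 = 9.8%.

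The risk over 160 weeks plus 90 days is 1 − 0.982 × 0.80 = 21.4%. The dependence on retention remains and is slightly weaker.

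**Step 3: the reverse reading.** Solving the Step 1 formula for λ at a crude 20% (12 of 60):

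| Retention | Rate per 100 patient-years | Week-160 risk |
|---|---|---|
| 90% | 7.7 | 21% |
| 50% | 10.4 | 27% |
| 10% | 20.1 | 46% |

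**Step 4: are the SAP 8.2.1 person-years the right denominator?** They stop at the last dose, whereas AEs are collected to about 90 days later. For 60 patients the difference is up to 60 × 90/365.25 = 14.8 patient-years. A patient who stops at Week 12 has 84 days of exposure and a further 90 days of AE follow-up, so more than half of that patient's observed time would be missing from the denominator.

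**The case against.** **The analysis may already be planned.** A reader might infer that the SAP contains no exposure-adjusted analysis. The documents do not support that. The part of Section 10 where general conventions would normally stand is lost, and an otherwise unused PYE abbreviation fits a use there, although it could be a leftover. This stands, and is why the first step is to check.

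**The percentages are not wrong.** The objective is to characterise safety in a single arm with no hypothesis test, and the share of patients with an event is a valid description of this cohort. No legible passage plans a comparison, so it would go too far to say that comparison is the only use of the figures. This stands, so the crude tables should stay.

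**Only 10.1.1 states percentages outright.** For SAEs, AESIs and discontinuations they follow from the general rule in SAP 5. This is true, but none of those sections names a time denominator or a period split either.

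**Part of the information is there.** Event counts are planned by SOC and PT, exposure is summarised, and SAP 6 tabulates discontinuations with reasons for Induction, for Extension to Week 52 and after Week 52. A reader could see early withdrawal and form a rough event rate. That rate would suffer the mismatch in Step 4, and the SAP does not plan it.

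**The size can be overstated.** At an assumed 10 events per 100 patient-years, 1 − e^(−0.10t) gives 2.3% at 12 weeks, 9.5% at 52 and 26.4% at 160, and a reader might infer that crude incidence could fall anywhere in that range. The low end needs every patient to leave at Week 12 and be followed no further. Adding 90 days (174 days in all) gives 4.7%. With high retention the effect is small.

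**A rate has its own weakness.** It assumes a constant hazard. For first-dose bradycardia and conduction events, long later exposure would dilute an early risk. Withdrawal related to prognosis would bias it as well. Splitting by period helps with the first problem, not the second.

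**Conclusion.** The point holds in a limited form. In the legible text, TEAEs, SAEs, AESIs and discontinuations have no time denominator and no split between Induction and Extension, over exposures from one dose to 160 weeks. The crude percentages are sound descriptions but do not estimate risk over a defined time. The size depends on retention: negligible if nearly all patients stay (19% against 20%), more than a halving if few do (8% against 20%, or about 10% against 21% with the 90-day follow-up counted). Those figures rest on assumed constant event and dropout rates.

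No hypothesis test, sample size or efficacy result is affected; only the reading of the Extension's primary objective is. The change is a worthwhile, low-cost addition, subject to what the lost lead-in says. A reader might also infer that SAP 8.2.1 already supplies everything needed. It does not, because its person-years end at the last dose and are not censored at first event.

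**What to change.** 1. Check the lead-in to SAP Section 10 and the start of 10.1. If exposure-adjusted or period-specific summaries are already defined there, cross-refer to them from 10.1.1 to 10.1.7 and check their time window against item 3.
2. Otherwise keep the crude tables. In 10.1.1, 10.1.4, 10.1.5 and 10.1.7 add patients with an event per 100 patient-years at risk, with exact Poisson 95% confidence intervals, for any TEAE, SAEs, AESIs and TEAEs leading to discontinuation. Report overall and separately for Induction and Extension, with the Extension figures based on patients who enter it.
3. Define time at risk from first dose (or period start) to first event or end of AE follow-up, closing Induction at the start of the Extension for those who continue. Use each patient's actual end of follow-up, since those who enter the open-label extension study at Week 160 skip the follow-up visits. Use the SAP 8.2.1 person-years only if the numerator is limited to on-treatment events.
4. Leave the Day 1 cardiac summaries in SAP 10.3 and 10.4 as planned, and note the constant-hazard assumption under the rate tables.

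Cost: modest programming of time to first event for each category and period, mostly from dates already collected, and extra columns in existing tables. Nothing planned is removed.

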10.1.2. Relationship of Adverse Events to Investigational drug

A summary of TEAEs by relationship to investigational drug will be presented in a table by incidence of occurrence. The potential relationships are “Unrelated”, “Unlikely”, “Possible”, “Probable”, and “Related”. A treatment-related TEAE is a TEAE with any relation to investigational drug other than “Unrelated” or “Unlikely”. In the TEAE by relationship table, if a

patient reports multiple occurrences of the same TEAE, only the most related occurrence will be presented. TEAEs that are missing relationship will be presented in the summary table as “Probable” but will be presented in the data listing with a missing relationship. A summary of treatment-related TEAEs by SOC and PT will also be presented.

10.1.3. Severity of Adverse Event

A summary of TEAEs by severity will be presented in a table. The potential severity levels are “Mild”, “Moderate”, and “Severe”. TEAEs will be classified by severity. In the TEAE severity table, if a patient reported multiple occurrences of the same TEAE, only the most severe occurrence will be presented. TEAEs that are missing severity will be presented in summary tables as “Severe” but will be presented in the data listing with a missing severity. A summary of severe TEAEs by SOC and PT will also be presented.

10.1.4. Serious Adverse Events

Criteria for determining SAEs are defined in the protocol.

A summary of treatment-emergent SAEs will be presented by SOC and PT, and also by SOC and PT and relationship to study drug. SAEs will also be listed separately.

10.1.5. Adverse Events Leading to Treatment Discontinuation

All TEAEs reported with an investigational drug action taken as “Permanently discontinued” will be summarized in a table by PT, and a listing excluding deaths will be presented.

10.1.6. Death

All patient deaths during this trial will be collected and presented in a listing. The information that is presented will include, at minimum, the date of first dose, date of last dose, date of last visit, date of death, cause of death, and relationship to study drug.

10.1.7. Adverse Events of Special Interest

Target treatment emergent adverse events of special interest (AESIs) will be closely monitored in the trial. AESIs include bradycardia and heart conduction abnormalities (e.g., symptomatic bradycardia, 2nd degree AV block, QT prolongation), pulmonary effects (significant decline in forced expiratory volume in 1 second [FEV₁], forced vital capacity [FVC], and diffusing capacity of the lung for carbon monoxide [DLCO] measurements), hepatic effects (confirmed liver function test (LFT) elevations > 3x ULN), macular edema based on abnormal OCT findings or visual signs/symptoms of new onset or worsening macular edema, serious or opportunistic infections and malignancies.

AESIs will be summarized by SOC and PT and presented in a listing.

10.2. Clinical Laboratory Evaluations

Laboratory assessments will be performed by a central laboratory. All summaries will be based on the standard international (SI) units provided by the central lab. Associated laboratory parameters such as hepatic profile, renal function, and hematology values will be grouped and presented together.

Summary tables for hematology, chemistry, and urinalysis including actual values and change and percent change values from Baseline will be presented for clinical laboratory tests collected as numeric values. These summaries will be provided for each visit, highest value, lowest value, and last value.

Hematology and blood chemistry values will be flagged as “low”, “normal”, or “high” relative to the normal ranges of the central laboratory. Categorical urinalysis values will be flagged as “normal” or “abnormal”. Categorical laboratory data will be summarized using shift tables where appropriate.

Laboratory data collected at unscheduled visits will be included in listings and will contribute to tables showing changes from Baseline to highest value, lowest value, and last value. The results from safety follow-up visit will not be included in the calculations of highest, lowest, and last values.

10.2.1. Hematology

The following laboratory tests will be included in hematology summary tables:

- Absolute Lymphocyte Count
- Basophils
- Basophils/Leukocytes
- Eosinophils
- Eosinophils/Leukocytes
- Ery. Mean Corpuscular HGB Concentration
- Ery. Mean Corpuscular Hemoglobin
- Ery. Mean Corpuscular Volume
- Erythrocytes
- Hematocrit
- Hemoglobin
- Leukocytes
- Lymphocytes
- Lymphocytes/Leukocytes
- Mean Platelet Volume
- Monocytes
- Monocytes/Leukocytes
- Neutrophils
- Neutrophils/Leukocytes
- Platelets

Actual values, change from baseline, and percent change from baseline will be summarized by visit. Shift tables from baseline, by visit, will be presented. The proportion of patients with abnormalities in Absolute Lymphocyte Count (ALC; $ALC < 200$ cells/uL; $ALC < 500$ cells/uL), Absolute Neutrophil Count (ANC; $ANC < 1000$ cells/uL), and Total WBC ($WBC > 20,000$ cells/uL) will be presented overall and by visit.

10.2.2. Blood Chemistry

The following laboratory tests will be included in the blood chemistry summary tables:

- Alanine Aminotransferase
- Albumin
- Alkaline Phosphatase
- Amylase
- Aspartate Aminotransferase
- blood Urea Nitrogen
- C-Reactive Protein
- Conjugated Bilirubin
- Creatinine
- Gamma Glutamyl Transferase
- Glucose
- Total Bilirubin

Actual values, change from baseline, and percent change from baseline will be summarized by visit. Shift tables from baseline, by visit, will be presented. The proportion of patients with abnormalities in Alanine Aminotransferase (ALT) and Aspartate Aminotransferase (AST) will be presented overall and by visit. Abnormalities in both ALT and AST will be presented for the following categories:

- > 1 x ULN;
- ≥ 2 x ULN;
- ≥ 3 x ULN;
- ≥ 4 x ULN;
- ≥ 5 x ULN;
- ≥ 8 x ULN; and
- ≥ 10 x ULN

A listing will present abnormal chemistry values for all patients.

10.2.3. Coagulation-related parameters

Coagulation panel results (central laboratory) will be summarized continuously for the Screening and Early Termination visits. A listing of abnormal coagulation-related parameters will be provided.

10.2.4. Urinalysis

The following laboratory tests will be included in the urinalysis:

- Specific Gravity
- pH
- Bilirubin
- Glucose
- Ketones
- Leukocytes
- Blood
- Protein
- Urobilinogen
- Urine Color and Appearance
- Nitrate
- Leukocyte Esterase

Actual values, change from baseline, and percent change from baseline will be summarized by visit for pH and Specific Gravity. Shift tables from baseline, by visit, will be presented for Bilirubin, Glucose, Ketones, Leukocytes, Occult Blood, Protein, Specific Gravity, Urobilinogen, and pH.

A listing of urinalysis values will be presented.

10.2.5. Pregnancy Testing and Serology Testing

Serum β -human chorionic gonadotropin (i.e., serum beta hCG) will be collected at Screening for females of childbearing potential. Between scheduled visits, monthly urine pregnancy tests (i.e., urine beta hCG) should be conducted by females of childbearing potential, and if the urine test is positive at the scheduled visit, it should be confirmed with a serum beta hCG test.

Serology testing will be collected at Screening for all patients and will include immunoglobulin G (IgG) antibodies to varicella-zoster virus (VZV), human immunodeficiency virus (HIV), immunoglobulin M (IgM) antibodies to hepatitis A virus (HAV), surface antigen of the hepatitis B virus (HBsAG), anti-hepatitis B core total antibodies (anti-HBc total), hepatitis B virus deoxyribonucleic acid (HBV DNA), and anti-hepatitis C virus (HCV) IgG/IgM.

Serum pregnancy, urine pregnancy, and serology results will be listed only.

10.3. Vital Sign Measurements

The following vital signs measurements will be collected for Day 1 (Baseline, Hour 1, Hour 2, Hour 3, Hour 4, Hour 5, and Hour 6, Week 4, Week 8, Week 12, Week 24, Week 36, Week 48, Week 52, and all visits subsequent to Week 52 according to the Protocol-defined schedule of vital signs assessments:

- Heart Rate (sitting; 'HR')
- Systolic Blood Pressure (sitting; 'SBP')
- Diastolic Blood Pressure (sitting; 'DBP')

The baseline value for a given patient in any tabulation or listing will be the lowest pre-dose value observed on Day 1.

Two separate continuous tabulations will be generated: for Study Day 1, actual values and change from baseline will be summarized continuously for Baseline, Hour 1, Hour 2, Hour 3, Hour 4, Hour 5, Hour 6, and Hour 7. Separately, for the post-baseline visits, the actual values and change from baseline will be summarized continuously for Week 4, Week 8, Week 12, Week 24, Week 36, Week 48, Week 52, and all visits subsequent to Week 52 according to the Protocol-defined schedule of vital signs assessments.

For Study Day 1, Heart Rate will be summarized categorically for the following categories for Day 1 for Hours 1, 2, 3, 4, 5, 6, and Minimum Overall:

- ≥ 65
- 60-64
- 55-59
- 50-54
- 45-49
- 40-44
- 35-39
- < 35

The proportion of patients requiring extended cardiac monitoring beyond Day 1, Hour 6, based on the criteria in Section 12.1.9. Guidelines for Monitoring Patients Taking Their First Dose of RPC1063 in the protocol, will be summarized categorically and will also be presented in a listing showing the criteria triggering a subject to be included in the listing. A listing of vital signs for the subjects who required extended cardiac monitoring per protocol criteria will be presented.

The number and percentage of patients who meet the criteria for clinically relevant abnormalities for HR, SBP, and DBP will be summarized by visit. The criteria for clinically relevant abnormalities are shown in the following table. All increases and decreases are relative to pre-dose on Day 1.

Table 7. Vital Sign Abnormality Cutoffs

Vital Sign	Criteria for Abnormalities
HR	> 120 bpm < 45 bpm
SBP	> 180 mmHg < 90 mmHg
DBP	> 105 mmHg < 50 mmHg

